## 11.0 Data Management and Statistical Analysis Plan

**General.** Baseline clinical and descriptive characteristics will be examined and compared between treatment groups using chi-square tests, Fisher's exact tests, t-tests, or Wilcoxon rank sum tests, as appropriate. Baseline characteristics that are significantly different between treatment groups will be included as model covariates. The primary analysis will focus on end-of-treatment (i.e., the final three weeks of the treatment phase) outcomes using an intent-to-treat framework.

**Randomization.** Both partners in each couple will be randomized to the same drug condition in a one-to-one manner utilizing a randomized permuted block design. In order to ensure that the treatment groups are balanced with respect to alcohol consumption (TLFB), a stratified randomization process will be used.

We plan to use REDCap and VA REDCap for data capture and management. REDCap (Research Electronic Data Capture) is a software toolset and workflow methodology for electronic collection and management of research and clinical trial data (Harris et al., 2008; Harris et al., 2007). REDCap provides secure, web-based flexible applications, including real time validation rules with automated data type and range checks at the time of entry. Exports are made available for several statistical packages including SPSS, SAS, SATA, R and Microsoft Excel. The system allows the research team to create and engage respondents using a variety of notification methods.

REDCap data dictionaries can be distributed for reuse at multiple institutions. A library of data dictionaries is made available for standards-based data collection forms and validated instruments (Obeid et al., 2012). The underlying database is hosted in a secure data center at MUSC/VA, a secure environment for data systems and servers on campus, and includes redundancy, failover capability, backups and extensive security checks. The system has several layers of protection including, user/group account management, "Data Access Groups" which allow data to be entered by multiple groups in one database with segmented user rights for entered data, audit trails for all changes, queries and reports, and Secure Sockets Layer (SSL) encryption.

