**Power and Sample Size.** This study is powered to detect moderate treatment group differences in percent days abstinent (PDA) and percent of days of heavy drinking (PDH), and relationship functioning as measured by the TLFB and DAS-7, respectively at end-of-treatment (weeks 9-12). Assuming 2-sided hypothesis testing and alpha levels of 0.05, we will have 80% power to detect treatment group differences with effect sizes of 0.6 in the presence of 30% attrition (n=70 couples) during the treatment phase. This approach is consistent with treatment group differences in PDA ( $d=0.59$ ) and PDH improvements ( $d=0.79$ ) in a prior ABCT trial (n=102), although we recognize that that trial compared individual therapy vs. ABCT (not ABCT  $\pm$  medication). In that study, PDA increased from  $34.98\% \pm 29.17\%$  to  $80.52\% \pm 27.75\%$  at the end of treatment in the ABCT group, and PDH decreased from  $56.83\% \pm 28.87\%$  to  $10.52\% \pm 22.16\%$  in the ABCT group. Incorporating an arcsine or other appropriate transformation to account for non-normality of these metrics will enable us to discern whether oxytocin enhances end of treatment PDA by an additional absolute 9% or greater (i.e., to 80.5% in the ABCT+ placebo group vs. 89.5% in the ABCT + oxytocin group) and whether oxytocin further decreases PDH by an absolute 6% or greater (i.e., to 10.5%

in the ABCT+ placebo group vs. 4.5% in the ABCT + oxytocin group). Another prior ABCT trial found that DAS-7 scores ( $21.1 \pm 6.7$ ) remain relatively constant throughout treatment. We will have 80% power to detect treatment group differences of 4 units of improvement in DAS-7 scores.

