To test hypotheses 1 and 2, a general linear modeling (GLM) framework will be used, treating end-of-treatment (weeks 9-12) PDA, PDH, and DAS-7 scores as dependent variables (in separate models), and treating treatment group (ABCT + oxytocin vs. ABCT + placebo) as the primary independent variable. Baseline values for PDA, PDH, and DAS-7 will be included as covariates, along with other potentially significant baseline characteristics. Since PDA and PDH may exhibit non-Gaussian distributional forms and/or zero-inflation, alternative modeling strategies (e.g., arcsine or Box-Cox transformations, two-part Hurdle models) may need to be explored. Model fit will be compared by examination of Likelihood Ratio chi-square values. If transformations are necessary, back-transformations will be used in conveying the model results. Similar modeling strategies will be used for secondary exploratory outcomes (described below).

**Hypothesis 3a:** PFC-AMY functional connectivity after treatment will be greater in participants who receive ABCT+ oxytocin compared to those who receive ABCT + placebo.

**Hypothesis 3b:** Baseline PFC-AMY functional connectivity in response to alcohol vs. neutral cues will predict the magnitude of change in alcohol use (PDA and PDH measured by TLFB in the final 3 weeks of treatment).

**Hypothesis 3c:** Baseline PFC-AMY functional connectivity in response to relationship conflict vs. neutral cues will predict amount of change in relationship functioning (IP DAS-7 scores in the final 3 weeks of treatment).

For hypothesis 3, preprocessing and analysis of fMRI data will use FSL v 5.0^148. Preprocessing includes rigid-body head motion correction of EPI images within a run, high-pass temporal filtering (sigma = 150 seconds), geometric distortion correction, slice timing correction, spatial filtering (FWHM = 6 mm) and registration to the MNI standard brain template. 'fsl\_motion\_outliers' will be used to determine head motion outliers which will be used a covariate of no interest in statistical analysis (together with the 6 rigid-body

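### The stated 80% two-sided power is about 70% on the plan's own inputs, and the 9-point PDA and 6-point PDH targets fall well short of an effect size of 0.6

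*Combined protocol and SAP*

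**What the plan says.** The power paragraph of Section 11.0 opens with "Assuming 2-sided hypothesis testing and alpha levels of 0.05" and then says "we will have 80% power to detect treatment group differences with effect sizes of 0.6 in the presence of 30% attrition (n=70 couples" remaining). For relationship functioning it quotes a DAS-7 SD of 6.7 from an earlier trial and concludes: "We will have 80% power to detect treatment group differences of 4 units of improvement in DAS-7 scores".

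For drinking it quotes end-of-treatment values from the couple-therapy arm of an earlier trial: PDA 80.52% (SD 27.75) and PDH 10.52% (SD 22.16). It says that an arcsine or other transformation will "enable us to discern whether oxytocin enhances end of treatment PDA by an additional absolute 9% or greater" (80.5% against 89.5%) and show "whether oxytocin further decreases PDH by an absolute 6% or greater" (10.5% against 4.5%).

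The Randomization paragraph of Section 11.0 allocates couples one to one. The analysis text for hypotheses 1 and 2 adds: "Baseline values for PDA, PDH, and DAS-7 will be included as covariates". Neither document section gives a baseline-outcome correlation, a within-couple correlation or a transformed-scale SD.

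**The concern.** Every input for the headline figure is printed, so a reader should be able to recover 80%, and cannot. The same shortfall appears in the DAS-7 statement, which makes a typing slip unlikely. Separately, the PDA and PDH differences sit beside SDs about twice as large as those needed to make them effects of 0.6.

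These are the primary outcomes, and Section 12.0 (Data Management and Analysis) says the study is powered for them. A null result would be read against a 20% chance of missing an effect of 0.6. On the stated inputs that chance is about 30%, and it is larger still at the 9- and 6-point targets. The 95% confidence intervals promised in Section 12.0 help interpretation but do not correct the stated power.

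**Working it through.** **Inputs from the documents.** Two-sided 0.05; d = 0.6; 70 couples, hence n = 35 per arm; DAS-7 difference 4, SD 6.7; PDA difference 9, SD 27.75; PDH difference 6, SD 22.16.

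**1. The stated 80%.** For a two-sample t-test, df = 2n − 2 = 68 and the noncentrality is d·√(n/2).

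- d = 0.6: 0.6 × √17.5 = 2.51. Two-sided power 69.7% (70.9% by the normal approximation). One-sided power 79.96%.
- DAS-7: d = 4/6.7 = 0.597. Two-sided power 69.2%, one-sided 79.6%.
- With no attrition (50 per arm), d = 0.6 gives 84.4%, so leaving attrition out does not explain the figure.
- 80% at d = 0.6 needs 45 per arm. At 35 per arm, 80% power is reached at d = 0.68, and 0.679 × 6.7 = 4.55 DAS-7 units.

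The one-sided match suggests a one-sided calculation under a two-sided label. It does not prove it.

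**2. Baseline adjustment.** In the planned model the effective d is d/√(1 − r²), with df 67, where r is the baseline-outcome correlation. No value of r is given, so these are assumptions:

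| r | Power at d = 0.6 |
|---|---|
| 0.3 | 74% |
| 0.47 | 80% |
| 0.5 | 81.5% |
| 0.6 | 87% |

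The r needed for 80% is 0.469 at d = 0.6 and 0.478 for 4 DAS-7 units.

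**3. Other ways to 80% for DAS-7 (assumed correlations).** Averaging four weekly scores multiplies the SD by √((1 + 3ρ)/4): power is 79.9% at ρ = 0.7 and 76.1% at ρ = 0.8. Using both partners multiplies it by √((1 + ICC)/2): power is 81.1% at ICC 0.5 and 76.1% at 0.7. The plan gives neither as its basis.

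**4. PDA and PDH, raw scale, unadjusted.** SDs implied by d = 0.6 are 9/0.6 = 15.0 and 6/0.6 = 10.0.

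- PDA, equal SDs: 9/27.75 = 0.324, power 27%. With the oxytocin-arm SD scaled by √(m(1 − m)), m being the arm mean as a proportion, it becomes 21.5. Then d = 9/√((27.75² + 21.5²)/2) = 0.363 and power is 32%.
- PDH: an SD of 22.16 is impossible at a mean of 4.5%, where the maximum is √(4.5 × 95.5) = 20.7. The scaled SD is 15.0, so d = 6/√((22.16² + 15.0²)/2) = 0.317 and power is 26%.

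**5. PDA and PDH, arcsine scale.** The documents give no distribution, so I simulated 20,000 trials per variant. The variants were beta and beta-binomial data, 21 and 28 days, placebo mean and SD as quoted, and three oxytocin-arm SDs per outcome.

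| Outcome | Oxytocin-arm SDs tried | Arcsine d | Power, arcsine t-test |
|---|---|---|---|
| PDA | 14.9, 21.5, 27.75 | 0.31–0.47 | 23–50% |
| PDH | 9.5, 15.0, 19.7 | 0.25–0.42 | 14–45% |

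The lowest powers come from the smallest oxytocin-arm SDs, the highest from the largest. At the best d (0.465 and 0.416), baseline adjustment would reach 80% only with r of about 0.73 (PDA) and 0.79 (PDH).

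**The case against.** The strongest reply is that the planned analysis is not an unadjusted t-test. It includes the baseline value, a correlation near 0.5 is plausible, and at 0.5 power is 81.5%. That stands as far as it goes: the trial's real power may well reach 80% at d = 0.6. But the power paragraph does not invoke the adjustment, no correlation appears anywhere, and 4/6.7 = 0.597 suggests that the authors used the raw SD.

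It can also be said that 70 couples is a pessimistic case, since the plan is intent-to-treat with multiple imputation. With 40 per arm, unadjusted power is 75.5%. But the plan ties its 80% to 70 couples, so the mismatch remains.

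The reply on PDA and PDH has more weight. The plan never says in so many words that 9 and 6 points equal d = 0.6 or carry 80% power; that is the natural reading of the paragraph. It relies on a transformation, so dividing raw differences by raw SDs is not its own calculation, and the arcsine results rest on assumed distributions. The top of the PDH range uses an SD of 19.7, close to the maximum of 20.7. Other methods can do better: in PDA simulations with a cluster of fully abstinent participants and a placebo SD of 26–27, a rank test gave about 58% where the arcsine test gave 43–47%. The hurdle models that the plan mentions are not covered here, and their power depends on the unstated share of participants at 0% or 100%. So the PDA and PDH figures are limited to the raw and arcsine scales. Within that limit, no variant tried reaches 80% without a high baseline correlation.

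**Conclusion.** The concern holds. On the printed inputs, two-sided power is 69.7% at d = 0.6 and 69.2% for 4 DAS-7 units, about 10 points below the stated 80%. This part needs no assumption beyond an unadjusted comparison with one score per couple. An unstated correlation of about 0.47–0.48 would restore 80%, so the fault is a figure that its stated basis does not support, not proof that the trial will have only 70% power.

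The 9-point PDA and 6-point PDH targets correspond to d of about 0.32–0.36 and 0.32 on attainable raw-scale SDs, and to at most 0.47 and 0.42 on the arcsine scale under the assumed distributions. An arcsine t-test would miss them about half the time or more. The planned analysis itself remains valid.

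**What to change.** Rewrite the power paragraph in one of two ways.

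- Report that 70 evaluable couples at two-sided 0.05 give about 70% unadjusted power for d = 0.6 and for 4 DAS-7 units, and that the 80% detectable effect is d = 0.68 (about 4.6 DAS-7 units).
- Or keep 80% and state what produces it: a baseline-outcome correlation of at least 0.47 (0.48 for DAS-7), or the use of repeated or both-partner DAS-7 scores with their correlations.

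For PDA and PDH, either replace 9 and 6 points with differences derived from stated transformed-scale SDs, or give the actual power for those differences, naming the model and the SD in each arm. Label the assessment window while doing so: the General paragraph of Section 11.0 uses "the final three weeks of the treatment phase", and the power and analysis text uses weeks 9–12. These may be meant as the same period, and the choice between 21 and 28 days does not change the conclusion above.

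The cost is one reworded paragraph and a less favourable or openly conditional power statement. Enrollment, endpoints and analysis stay as they are.

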**Missing Data.** We will examine whether participants who complete treatment differ from those who drop out on key variables, and whether variables on which they differ interact with treatment group to affect outcome measures. Because participants will be randomized to treatment condition, it is unlikely that missing data will produce biased estimates of treatment effect, as observed and unobserved covariates will theoretically be balanced across treatment groups. In addition, less than 10% missing data generally has little impact on power and does not introduce bias, regardless of the missing data mechanism. If the percent missing data are greater than 10%, multiple imputation techniques will be used to examine the influence of missing data on our study findings. If data are missing not at random, propensity score methods will be considered for data imputation. In the propensity score method, first the distribution of the missing indicator variable given the observed data is modeled to derive a propensity score. Then observations are grouped on these propensity scores and an approximate Bayesian bootstrap imputation is applied to each group.

Hypotheses and statistical approaches for testing each are described below.

**Hypothesis 1:** The ABCT + oxytocin group will demonstrate significantly greater reduction in alcohol consumption from baseline to end of treatment as compared to the ABCT + placebo group (PDA and PDH measured by TLFB).

**Hypothesis 2:** The ABCT + oxytocin group will demonstrate significantly greater improvement in relationship functioning (measured by DAS-7) from baseline to end of treatment as compared to the ABCT + placebo group.

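### The missing-data plan wrongly rules out bias below 10% missing, has no analysis for data missing not at random, and implies a completer primary analysis that is not reconciled with intent-to-treat

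*Combined protocol and SAP*

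**What the plan says.** Section 11.0, Missing Data, opens with an argument from randomization: "Because participants will be randomized to treatment condition, it is unlikely that missing data will produce biased estimates of treatment effect", on the ground that covariates should be balanced between arms. It then sets a threshold: "less than 10% missing data generally has little impact on power and does not introduce bias, regardless of the missing data mechanism". Above 10%, "multiple imputation techniques will be used to examine the influence of missing data on our study findings". For MNAR data, "If data are missing not at random, propensity score methods will be considered for data imputation". The method is described as follows: "first the distribution of the missing indicator variable given the observed data is modeled to derive a propensity score", after which cases are grouped by score and an approximate Bayesian bootstrap fills in values within each group. A comparison of completers with drop-outs is also planned.

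Three other paragraphs of Section 11.0 bear on this. General says the primary analysis takes end-of-treatment "outcomes using an intent-to-treat framework". The model for Hypotheses 1 and 2 is a general linear model (GLM) "treating end-of-treatment (weeks 9-12) PDA, PDH, and DAS-7 scores as dependent variables", with baseline as a covariate. Power and Sample Size counts its detectable effect "in the presence of 30% attrition (n=70 couples) during the treatment phase".

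Section 14.0, Safety and Monitoring Plan, lists increased drinking that calls for more intensive treatment among the reasons for withdrawing a participant from the study.

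**The concern.** The threshold sentence says the missing-data mechanism does not matter when little is missing. The mechanism is what decides whether bias arises. The percentage limits how large the bias can be, but does not make it zero.

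The randomization sentence is weak reasoning. Randomization balances everyone who was randomized. It does not protect a comparison among those still observed at weeks 9-12 if leaving is related to drinking and to arm.

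The MNAR step cannot do the job it is given. Missingness that depends on the unseen value itself cannot be corrected by matching on what was seen and drawing from people who stayed.

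The practical stake lies at the planned 30% attrition. Imputation there has only an exploratory role, so the reported primary estimate would rest on completers while being labelled intent-to-treat. Some loss can depend on the primary outcome, because worsening drinking is itself a reason for withdrawal. How often that will happen is not stated.

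**Working it through.** **The plan's own count.** 100 couples x (1 - 0.30) = 70 couples, or 35 per arm at one-to-one allocation. This reproduces. The figure counts only couples who remain.

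**Reading the paragraphs together.** Power counts 70 couples. The GLM needs one end-of-treatment value per unit and does not use the weekly history. Missing Data gives imputation a probing role only. The consistent reading is a GLM on completers as primary, with imputation as a sensitivity analysis above 10%. General says intent-to-treat, and no paragraph says how a randomized couple without a weeks 9-12 value enters the estimate.

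**The power half of the threshold sentence.** With a standardized effect of 0.6, two-sided alpha 0.05 and the normal approximation, 50 per arm gives 0.6 x sqrt(50/2) - 1.96 = 1.04, or 85.1% power. With 10% loss (45 per arm), 0.6 x sqrt(45/2) - 1.96 = 0.89, or about 81%. That half is reasonable.

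**The bias half.** Let m be an arm's loss rate and g the retained-minus-lost gap in mean outcome. The full-arm mean is (1 - m) x retained + m x lost, so the retained mean differs from it by m x g. The shift in the treatment difference is m1 x g1 - m0 x g0.

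Inputs, from the prior-trial figures in Power and Sample Size:
- Percent days abstinent (PDA): 80.52 - 34.98 = 45.54 points.
- Percent days of heavy drinking (PDH): 56.83 - 10.52 = 46.31 points.
- Assumption, not in the plan: lost couples sit at that trial's baseline and retained couples at its end value.
- Targets: 9 points PDA and 6 points PDH.

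| Overall loss | By arm | PDA shift | PDH shift |
|---|---|---|---|
| 9% | 9% / 9% | 0 | 0 |
| 9% | 14% / 4% | 0.10 x 45.54 = 4.6 | 0.10 x 46.31 = 4.6 |
| 30% | 30% / 30% | 0 | 0 |
| 30% | 36% / 24% | 0.12 x 45.54 = 5.5 | 0.12 x 46.31 = 5.6 |

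The higher-loss arm looks better than it is, so the sign follows whichever arm loses more. Halving the gap halves each figure. Equal loss rates alone do not guarantee zero: if the gap differs between arms by 10 to 20 points, the shift is 0.09 x 10 to 0.09 x 20 = 0.9 to 1.8 at 9% loss, and 0.30 x 10 to 0.30 x 20 = 3 to 6 at 30%.

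These figures are unadjusted. Relationship functioning (DAS-7) gets no figure because the plan reports its prior-trial scores as roughly constant and gives no gap to use.

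**The MNAR step.** Within a propensity group the bootstrap draws from observed members, so the expected imputed value is the observed mean of that group. If lost members of the group are worse than retained members by some amount, all of that amount stays in the estimate. The step is valid only when no such difference exists given the observed data, which is MAR.

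**Scale for a tipping-point analysis at 30% loss.** If only imputed oxytocin values are shifted, removing the whole target takes 9 / 0.30 = 30 points of PDA or 6 / 0.30 = 20 points of PDH.

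**The case against.** Five points can be made for the plan.

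- **The randomization sentence is hedged.** This stands. It says bias is unlikely and appeals to balance in theory. A reader might take it as a second flat denial of bias, but the text does not support that. It is a poor argument, not a false claim.
- **The 10% rule may never operate.** This largely stands. With 30% attrition planned, imputation would be triggered unless retention is far better than expected. It does not rescue the sentence, and it moves the weight to what happens above 10%.
- **A primary analysis can be inferred.** This stands too. A reader might conclude that nothing determines the primary estimate, but the power count, the GLM and the role given to imputation together point to completers. The defect is that this is implied and conflicts with the intent-to-treat label.
- **Blinding should make loss similar in the two arms.** This is fair, and zero bias is possible. It is not assured if oxytocin affects who stays.
- **Less may be missing than 30% attrition suggests.** Drinking is recorded by retrospective calendar (Section 3.0), which Table 1 repeats at 3 and 6 months, and treatment drop-out need not end follow-up. Weekly drinking data in the propensity model could also make MAR more plausible. Both could shrink the problem. The plan commits to neither, and it states no later drinking assessment for participants withdrawn from the study.

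Section 12.0 has the investigator and a statistician examine the outcomes database for missing data, and puts retention and disposition in the yearly monitoring report. That is useful oversight, but it does not define the estimate.

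**Conclusion.** The concern holds in this form. The statement that under 10% missing data cannot bias the result is wrong. The randomization argument is weak. The only step offered for MNAR data assumes MAR. The implied completer analysis is not reconciled with intent-to-treat. These follow from the text, and confidence in them is high.

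The consequence is much less certain. Under the assumption that lost couples return to the prior trial's baseline, unequal loss of 36% versus 24% would shift PDA by 5.5 points (target 9) and PDH by 5.6 (target 6). At 9% overall, a 14% versus 4% split shifts PDA by 4.6. Loss by arm and the outcomes of lost couples are unknown, so the actual shift may be zero or of either sign.

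A reader might infer that the trial's result will be biased, or that loss below 10% could overturn it. The documents support neither. They show only that the plan dismisses a bias it cannot exclude and has no analysis to measure it. This should be fixed before unblinding.

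**What to change.** In Section 11.0:

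1. Delete the 10% no-bias sentence and the 10% trigger, and drop the randomization argument.
2. State that the primary analysis includes all randomized couples as randomized, whatever the percentage missing, under one pre-specified MAR method. One suitable choice is multiple imputation using arm, baseline and the weekly drinking and DAS-7 data already collected, followed by the planned GLM.
3. Stop presenting the propensity step as MNAR handling. Replace it with a pre-specified delta-adjusted (tipping-point) sensitivity analysis by arm, with the range fixed in advance and imputed PDA and PDH kept within 0-100.
4. Say whether drinking data gathered at later visits may be used to fill weeks 9-12.

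Withdrawal criteria are unchanged, and no new visits or data are needed. The cost is SAP wording and some extra programming. That includes making imputation and delta shifts work with whatever transformation or hurdle model is chosen for PDA and PDH. The interval may be slightly wider.

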## **5.0 Number of Subjects**

100 couples will be enrolled (200 total participants).

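### The optional propensity-score imputation does not keep donors within arm; read literally, at 30% equal dropout it would shrink the sensitivity estimate by roughly 11–17% (arm in the score) or about 30% (arm left out)

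*Combined protocol and SAP*

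**What the plan says.** Section 11.0, Missing Data, has two tiers. Above 10% missing, unspecified multiple imputation is used to see how far missing data influence the findings. If data are judged missing not at random, a propensity-score method would be considered. It is the only imputation procedure described step by step: "first the distribution of the missing indicator variable given the observed data is modeled to derive a propensity score", and "Then observations are grouped on these propensity scores and an approximate Bayesian bootstrap imputation is applied to each group". The variables in the score, the number of groups and the role of treatment arm are not given.

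Under Power and Sample Size the plan allows for "effect sizes of 0.6 in the presence of 30% attrition (n=70 couples) during the treatment phase", which is three times its own 10% trigger, so some imputation is to be expected.

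The tests of Hypotheses 1 and 2 use a linear model of each end-of-treatment outcome with the baseline value as covariate, "treating treatment group (ABCT + oxytocin vs. ABCT + placebo) as the primary independent variable". That text does not mention imputed data.

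**The concern.** The score describes who is missing, not what the missing value would have been. Couples with the same estimated chance of dropping out share a donor group whatever their arm. Where arms share a group, the imputed values carry little or none of the treatment difference, yet the analysis model then estimates that difference from the completed data. The imputation omits the one association that the analysis tests.

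Putting arm into the score is not enough. When dropout is similar by arm, its coefficient is near zero and the groups still mix arms. The dilution therefore occurs even under missing completely at random (MCAR), where leaving the data unimputed gives no bias.

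What is at stake is the check itself. It would be called on when dropout looks informative, and a shrunken estimate there could be read as evidence that a real oxytocin effect is fragile.

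**Working it through.** **Inputs from the plan.** 100 couples (Section 5.0) allocated 1:1, so 50 per arm. 30% attrition: 100 × 0.7 = 70 couples, 35 observed per arm. DAS-7 SD 6.7 and difference 4 units, so 4/6.7 = 0.597 SD.

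**Assumptions not in the plan.** One record per couple, Gaussian DAS-7, baseline–outcome correlation 0.5, logistic score, five or ten equal groups, analysis of covariance (ANCOVA) on arm and baseline.

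**The plan's own figure.** It gives none for imputation bias. Its nearby 80% power does not reproduce unadjusted: Φ(0.6·√(35/2) − 1.96) = Φ(2.51 − 1.96) = Φ(0.55) ≈ 70.9%. It needs an unstated baseline correlation of about 0.45. That is a separate matter; only the attrition, SD and difference are used here.

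**Step 1, formula.** Let m be the missing fraction, equal in both arms, and q the share of imputed values drawn from the opposite arm. Observed values carry the full difference Δ. Imputed values carry (1 − q)Δ − qΔ = (1 − 2q)Δ. The completed-data difference is

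(1 − m)Δ + m(1 − 2q)Δ = Δ(1 − 2mq).

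- Arm not in the score: q = 0.5, so 4 × (1 − 2 × 0.3 × 0.5) = 4 × 0.7 = 2.8 units, a 30% loss.
- Within-arm donors: q = 0, so no loss.
- Arm in the score, equal dropout: simulated q was 27–47%. At 0.27, 4 × (1 − 0.162) = 3.35, a 16% loss. At 0.47, 4 × (1 − 0.282) = 2.87, a 28% loss.

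**Step 2, simulation** (true difference 4; 30% missing overall; percentages pair the two arms' dropout):

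| Dropout | Score and groups | Mean estimate | Loss |
|---|---|---|---|
| 30/30, MCAR | baseline + arm, 5 | 3.33–3.35 | 16–17% |
| 30/30, MCAR | baseline + arm, 10 | 3.57 | 11% |
| 30/30, MCAR | baseline only, 5 | 2.82 | about 30% |
| 30/30, depends on baseline | baseline + arm, 5 | 2.86–2.99 | 25–29% |
| 25/35, unrelated to baseline | baseline + arm, 5 | 3.48 | 13% |
| 20/40, unrelated to baseline | baseline + arm, 10 | 3.84 | 4% |
| 25/35, depends on baseline | baseline + arm, 5 | 2.66 | 34% |
| Any of these, within-arm donors | – | 3.9–4.1 | about 0% |

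Repeat runs on the standardised scale (d = 0.6, MCAR, arm in the score) gave 13.7% with ten groups and 14.7–16.2% with five. Adding an interim outcome or more covariates to the score raised the loss to 21.5% and 25.6%. The largest loss in any pattern was 37%. With 20/40 dropout and ten groups, one set of runs gave 2.0% (Monte Carlo error 1.2 points), so 4% is not a hard floor. Direction also matters when missingness depends on baseline. Where high-baseline couples drop out more, estimates were 3.2–4.0 if oxytocin couples also drop out more, and 2.6–2.9 if placebo couples do.

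**Step 3, comparators.** Complete-case ANCOVA returns about 4.0 under MCAR. It also stays nearly unbiased when missingness depends only on baseline, because baseline is in the model. Power under 30/30 MCAR was 62% for pooled donors against 78% for within-arm donors.

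**Step 4, the case that triggers the method.** With simulated missing-not-at-random (MNAR) dropout at 30%, pooled donors lost 17–35% and complete cases 6–10%. Within-arm donors still lost 4.6%. Drawing within arm removes the dilution but does not make this an MNAR method, because the score uses observed data only.

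**The case against.** The strongest reply is that the plan commits to very little. The method would only be considered, only if data are judged missing not at random, and imputation serves to examine the influence of missing data. A reader might infer that the trial's treatment effect will be shrunk by a sixth to a third. The documents do not support that: the section on Hypotheses 1 and 2 never says that the main models are fitted to imputed data. This part of the reply stands.

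Second, mixing of arms is inferred from silence, and running the procedure separately by arm would fit the same sentence. That is fair. But the only grouping variable named is the score, so a programmer following the text would pool arms, and the choice would otherwise be made after data are seen.

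Third, the size depends on things the plan does not give: the score's variables, the number of groups and the dropout pattern. This also stands, so no single percentage should be quoted as general. Nor do the simulations cover percent days abstinent or heavy drinking, which the plan itself expects may be non-Gaussian or zero-inflated.

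**Conclusion.** The point holds as a defect in an optional sensitivity analysis. As written, its donor groups are not restricted by arm. At 30% attrition with equal dropout under MCAR, the estimate is attenuated by roughly 11–17% with arm and baseline in the score (5–10 groups) and by about 30% without arm: 4 DAS-7 units become about 3.3–3.6, or 2.8. Elsewhere the loss runs from about 4% to 37%. These figures rest on the assumptions listed in the working.

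A reader might go further and conclude that the primary result is biased, or that a 15–35% loss is to be expected whatever the dropout pattern. Neither follows: the main estimate is not tied to this imputation, and with arm in the score and unequal dropout unrelated to baseline the loss can be small. What remains is that, in the equal-dropout cases examined, the check gives a worse answer than no imputation and could wrongly cast doubt on a real effect. It should be corrected, but it does not undermine the trial.

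**What to change.** Add to the Missing Data paragraph: *Propensity groups will be formed, and donors drawn, separately within each treatment arm, using about three groups per arm.* Alternatively: *Missing end-of-treatment outcomes will be multiply imputed from a model that includes treatment arm and the baseline value of the outcome.*

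Label whichever is chosen as a missing-at-random analysis. Because the propensity method is the plan's only provision for data missing not at random, do not simply delete or relabel it. Specify a separate analysis for that case, for example shifting the imputed values by a pre-stated range in each arm.

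The cost is SAP wording and a few lines of code, with no new data or participants. The small downside is smaller donor pools: about 35 observed couples per arm, or about 35/3 ≈ 12 per group. Regression imputation that included arm and baseline performed about as well in simulation (3.9–4.0 units at 30% missing). A model using all the weekly values was not tested and should be tried out at this sample size before it is written in.
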